6.4.1 Analysis variables

The analysis variables defined for all participants in the main study cohort consist of baseline participant characteristics, longitudinal measures of risk of infection, SARS-CoV-2 infection and seroconversion and COVID-19 disease status, and immune response biomarkers. For individuals diagnosed with SARS-CoV-2 infection, post-infection variables will include various summaries of VL, the full genome sequence of the infecting virus, and the infection status of and relationship to each of their contacts enrolled in the PCC and CACC. For contacts enrolled in the PCC and CACC, variables consist of baseline participant characteristics, SARS-CoV-2 infection and seroconversion status, risk factors around time of exposure to main study participant (if infected) and relationship to the referring main study participant.

6.4.2 Baseline comparability and comparability over study follow-up

Groups of main study participants will be compared with respect to baseline participant characteristics using descriptive statistics.

Given that the study is open-label, and the associated potential for differences between randomized arms with respect to retention, compliance with study procedures, ascertainment of endpoints, and variables associated with exposure to SARS-CoV-2, these measures will be compared between randomized arms over time using methods fully described in the SAP. Given that participants self-select into the Vaccine Declined Group, similar methods will be used to evaluate potential differences between this group and those randomized to Immediate vaccination or Standard of Care. Imbalances between groups will influence the analysis choices as described below.

6.4.3 Vaccine efficacy (VE) analyses against SARS-CoV-2 infection

The time origin for all analyses of SARS-CoV-2 infection is enrollment. We define the time of diagnosis of the SARS-CoV-2 infection endpoint as the collection time of the first daily swab with a positive PCR test. The time of diagnosis of lab-confirmed clinical COVID-19 disease is the first time of reported qualifying COVID-19 symptoms that occurs simultaneously or after the diagnosis of the SARS-CoV-2 infection endpoint. The time of diagnosis of asymptomatic SARS-CoV-2 infection is the collection time of the first sample with a positive PCR test result or seroconversion without any prior or subsequent reporting of symptoms that led to confirmation of a COVID-19 disease endpoint. The time of diagnosis of SARS-CoV-2 seroconversion is the collection time of the first sample seropositive for SARS-CoV-2, for participants SARS-CoV-2 seronegative at baseline; the SAP will specify criteria for defining seroconversion (re-infection)

for individuals SARS-CoV-2 seropositive at baseline. The failure times of participants never observed to be diagnosed with a given clinical endpoint will be right-censored at the date of last contact at which endpoint status was assessed or study termination. The failure times of participants reporting receipt of COVID-19 vaccination outside the study will be right-censored at the date of first outside vaccination.

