6.4.3.2 Secondary VE Analyses

The primary analysis of VE against SARS-CoV-2 infection will be repeated in the FAS and D29- sets but including baseline seropositive participants [Secondary Objective 5]; and in the PP set [Secondary Objective 9]. The same methods also apply to evaluating VE against seroconversion [Secondary Objective 2] and VE against COVID-19 disease [Secondary Objective 3]. Additional secondary VE analyses will be conducted where the time of SARS-CoV-2 infection diagnosis is defined as the earliest of the first positive SARS-CoV-2 test result based on either PCR testing of nasal swabs or external SARS-CoV-2 testing.

While the primary analysis of VE against SARS-CoV-2 infection will censor the follow-up time of participants who receive outside COVID-19 vaccination at the time of first outside vaccination, a secondary analysis will be performed that includes infection events and person-time that accrue following outside vaccination with the Moderna COVID-19 Vaccine. Participants receiving outside vaccination other than Moderna COVID-19 Vaccine will continue to be censored at the time of outside vaccination. A time-varying Cox model will be used for inference, per methods in the study SAP.

The asymptomatic SARS-CoV-2 infection endpoint [Secondary Endpoint 8] is defined by the PCR tests of daily swabs and serologic diagnostic testing schedule at month 0, 2, and 4. The occurrence of a COVID-19 disease event is a competing risk because the occurrence of COVID-19 disease precludes the possibility of occurrence of a subsequent asymptomatic SARS-CoV-2 infection event. Therefore, VE against asymptomatic SARS-CoV-2 infection will be assessed using methods accounting for COVID-19 disease as a competing risk. The SAP will provide details.

Vaccine efficacy against the infection and disease endpoints as measured by the reduction in the cumulative incidence of the endpoint by Month 4, will also be evaluated using the Nelson-Aalen estimator of cumulative incidence. This analysis does not rely on the proportional hazards assumption and has a simple interpretation that lends itself to understanding of population effects.

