Appendix I Visit windows

Main Cohort, Immediate Vaccination, Visit Windows

Visit Number	Visit Type	Lower Allowable Window	Lower Target Day	Target Day ¹	Upper Target Day	Upper Allowable Window
01.0	Screening	-56	-		-	0
02.0	Enrollment/Randomization ²	-	-	1	-	-
03.0	Vaccination 2	-	-3	29 ³	+7	+14
04.0	Month 2 Follow-up	-	-7	57	+7	+14
05.0	Month 4 Follow-up	-13	-7	113	+14	+56

1. Target dates are relative to Visit 2.0 (Enrollment/Randomization), except for cases described in footnote 3.

2. Completion of post enrollment activities may occur up to approximately 7 days post enrollment (see Section 9.3).

3. In the event that Vaccination 1 occurs on a different day than Visit 2.0 (Enrollment/Randomization), Visit 3.0 target dates are relative to date of Vaccination 1.

Main Cohort, Standard of Care and Vaccine Declined, Visit Windows

Visit Number	Visit Type	Lower Allowable Window	Lower Target Day	Target Day ¹	Upper Target Day	Upper Allowable Window
01.0	Screening	-56	-		-	0
02.0	Enrollment/Randomization ²	-	-	1	-	-
04.0	Month 2 Follow-up	-	-7	57	+7	+14
05.0	Vaccination 1 ³	-13	-7	113	+14	+28
06.0	Vaccination 2 ^{1,3}	-	-3	141	+7	+14

1. Target dates are relative to Visit 2.0 (Enrollment/Randomization), except visit 06.0, which is relative to visit 05.0.

2. Completion of post enrollment activities may occur up to approximately 7 days post enrollment (see Section 9.5).

3. Vaccination visits only apply to participants who have not received COVID-19 vaccine outside the study and for participants in the Vaccine Declined Group who request to be vaccinated.

Case-Ascertained Close Contact (CACC) Cohort and applicable Prospective Close Contact (PCC) participants¹, Visit Windows

Visit Number	Visit Type	Lower Allowable Window	Lower Target Day	Target Day ²	Upper Target Day	Upper Allowable Window
200.0	Enrollment	-	-	1	-	-
201.0	Initial blood specimen collection		-2	3	+1	+4
202.0	Day 29 Follow-up	-	-7	29	+14	+28

1. Applicable to PCC participants when they (or their Main study contact) tests positive for SARS-CoV-2.

2. Target dates are relative to Visit 200.0 (Enrollment).

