3.2 Statistical Analysis Issues

3.2.1 Time scales

The analysis will utilize two different time scales. “Calendar time” will be defined as time since enrollment of the first study participant. “Study time” will be defined as time from either the first

nasal swab (if the first swab result was negative) or 90 days after the first swab (if first swab positive). Note that while randomization would be the ideal origin for study time, some participants did not begin swabbing until days or even weeks into the study, and infection status and timing of infection cannot be determined prior to the initiation of swabbing.

3.2.2 *Incident infection*

An incident SARS-CoV-2 infection will be defined as the first instance of a positive PCR result that follows at least one negative PCR result. Therefore, for participants who are baseline SARS-CoV-2 positive (i.e. seropositive at first blood collection or PCR positive on first swab), an incident infection occurs only 90 days after the first swab and once there is at least one negative PCR followed by a positive PCR.

3.2.3 *Seroconversion*

A seroconversion event will be defined as the first instance of a positive serology result that follows at least one negative serology result.

3.2.4 *Censoring approaches*

The following analyses will use the following censoring approaches (as specified in analytical approach). For the primary endpoint, “test” refers to a PCR test of a nasal swab. For the secondary endpoint of seroconversion, “test” refers to serology of a blood sample.

- ITT censoring: In the SoC arm, follow-up time is censored at the last negative test prior to end of study vaccination or the last negative test if the participant is not vaccinated on study (both are ignored if the first positive test occurs after the last negative test). In the Immediate Vaccination arm and the Vaccine Declined group, follow-up will be censored at the last negative test (ignored if the first positive test occurs after the last negative test). The timing of any test is considered to be the day on which the assay was collected, where day is defined from 3AM to 3AM of local time of the site.

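### Unequal Month 4 serology windows combined with draw-date Cox timing can bias VE against seroconversion when draw days differ between arms

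*Protocol*

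**What the plan says.** - **Visit windows (Protocol Appendix I).** For Immediate Vaccination, Visit 5 reads "Month 4 Follow-up -13 -7 113 +14 +56". For Standard of Care and Vaccine Declined, Visit 5 is labelled as the first vaccination. It has the same target day, target window and lower limit, but an upper limit of +28. The Month 2 visit is the same in both tables: "04.0 Month 2 Follow-up - -7 57 +7 +14".
- **Serology schedule (Protocol 6.4.3.2).** Testing follows a "serologic diagnostic testing schedule at month 0, 2, and 4", so Month 4 is the last scheduled draw.
- **Event and censoring times (Protocol 6.4.3).** "The time of diagnosis of SARS-CoV-2 seroconversion is the collection time of the first sample seropositive for SARS-CoV-2". Participants without the event are "right-censored at the date of last contact at which endpoint status was assessed or study termination". The time origin is enrollment.
- **Model (Protocol 6.4.3.2).** "The same methods also apply to evaluating VE against seroconversion", meaning the Cox regression of the primary analysis.
- **SAP.** Section 2.2 keeps Secondary Objective 2. Section 3.2.3 defines seroconversion. Section 3.2.4 sets censoring for "the secondary endpoint of seroconversion" and times each test by its collection day. Section 7 moves efficacy analyses to calendar time. Section 9 covers transmission, disease and variants, and gives no model for VE against seroconversion.

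Neither document gives an interval-censored method or a common draw window for this endpoint. The interval-censored time in SAP 3.2.5 concerns outside vaccination.

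**The concern.** With two scheduled post-baseline draws, a recorded seroconversion time is a visit date, and the infection may have occurred weeks before. An Immediate participant drawn on D150 is counted as at risk and event-free throughout the days on which Standard of Care is drawn, even if already seroconverted. If that draw is positive, on the enrollment time scale no Standard of Care participant remains in the risk set, so the event adds nothing to the comparison. Immediate events are lost while Immediate risk sets stay large, and the estimated hazard ratio falls for a reason unrelated to the vaccine.

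Secondary Objective 2 is at stake, and so is the serology component of the asymptomatic infection endpoint (Secondary Objective 8).

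**Working it through.** **Windows.** Immediate: 113 − 13 = D100 to 113 + 56 = D169. Standard of Care: D100 to 113 + 28 = D141. Shared target window: 113 − 7 = D106 to 113 + 14 = D127. The upper limits differ by 28 days. Month 2: D50 to D71 in both.

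**Check of the plan's rates.** The documents give no seroconversion count. The nearest figure is the 225 post-Day 29 PCR infections in Protocol 6.1 (4% over 16 weeks, VE 50%). Inputs are from Table 6-2.
- n = 6,000 × 0.90 × 0.98 = 5,292 per arm; λ = −ln(0.96)/16 = 0.002551 per week; loss c = −ln(0.95)/16 = 0.003206 per week.
- Unvaccinated, weeks 4–16: n · exp[−4(λ+c)] · λ/(λ+c) · {1 − exp[−12(λ+c)]} = 153.0.
- Vaccinated, with hazard λ/2 from day 14: 77.3.
- Total 230.3, which is 2.3% above 225. The same incidence is used below.

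**Mechanism by hand.** Let f be the share of Immediate drawn after D141, and u the share of shared-window draws already done. Let r be the true ratio of positive proportions. On the enrollment scale, with few events, the hazard ratio seen at Month 4 is approximately

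r × (1−f)(1−u) / [(1−f)(1−u) + f].

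With r = 0.50 and f = 0.20 (assumed):
- u = 0: 0.50 × 0.80/1.00 = 0.40
- u = 0.5: 0.50 × 0.40/0.60 = 0.33
- u = 0.9: 0.50 × 0.08/0.28 = 0.14

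With f = 0 the ratio stays at 0.50. Month 2 draws, with equal windows, also give 0.50. The fitted value lies between the two visits.

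**Simulation A, late Immediate draws.** Constant 4% incidence over 112 days in controls; 14-day lag to seroconversion (assumed); Month 2 draw D50–D71; Month 4 draw evenly over D100–D141, except a share f of Immediate evenly over D142–D169; Cox model with Breslow ties.

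| True VE | Time scale | f = 10% | f = 20% |
|---|---|---|---|
| 50% | enrollment | about 58–59% | about 65% |
| 50% | calendar, 28-day enrollment | about 58% | about 64% |
| 50% | calendar, 120-day enrollment | about 53% | about 55% |
| 70% | enrollment | 76% | 80% |
| 0% | enrollment | about 18% | about 28–29% |

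With f = 0, a true 50% is recovered to within about one point.

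**Simulation B, draws centred on the target window.** Draws in D106–D127, except a late share spread from D128 to each arm's own upper limit; no lag; enrollment time unless stated; true VE 50%.
- None late: 49.4%.
- Same share late in both arms: 54.1% (10%), 59.6% (25%). On calendar time the 25% case gives 59.0% with 28-day and 52.4% with 180-day enrollment.
- Only Immediate late, 25%: 65.2%.
- Only Standard of Care late, 25%: 30.6%, so the bias reverses.

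**Alternatives.** An exponential interval-censored likelihood gives 48–51% for a true 50% in every Simulation B scenario. The discrete-visit Cox analysis, counting Month 4 draws only to D141, gives 49–50% for a true 50% and about 1% for a true 0% under Simulation A. Crude cumulative risk does not solve the problem. It moves the other way (48.2% with 25% late in both arms, 46.3% with 25% late in Immediate only), because later draws capture more Immediate infections.

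**The case against.** The strongest reply is that the windows are outer tolerances. Target day, target window and lower limit are the same, and if sites keep to the target window nothing goes wrong. That stands. A reader might infer that the visit schedule itself inflates the serological VE. The documents do not support this: they permit later Immediate draws but give no share of them, and the direction depends on which arm runs late. An even spread of Immediate draws over D100–D169 would put 28 of 70 days (40%) after D141, and nothing in Appendix I suggests that pattern.

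Second, the SAP works on calendar time. With staggered enrollment, later Standard of Care enrollees are still at risk when late Immediate positives appear, so the bias shrinks as enrollment spreads. That stands, but with the design's 4-week enrollment most of it remains.

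Third, the SAP gives no seroconversion VE model, and its introduction says some objectives cannot be addressed. So the point applies only if this VE is estimated. The SAP nevertheless keeps the objective, event and censoring, which leaves the protocol's Cox model as the only stated method.

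Fourth, Protocol 6.4.2 compares endpoint ascertainment between arms, and 6.4.3.1 adjusts for differential censoring. These may reveal unequal draw days. Reweighting for censoring does not correct an event time that is set by the draw.

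A reader might also take serology to be the trial's check on infections missed by swabs. No passage says so, and Protocol 2.1 and 2.4 argue instead that serology misses infections.

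**Conclusion.** The concern holds conditionally. The unequal upper limits, draw-date event times and Cox model together make VE against seroconversion depend on when each arm is drawn. With 10–20% of Immediate draws after D141, a true 50% reads about 58–65% on enrollment time. On calendar time it reads about 58–64% with 28-day enrollment and 53–55% with 120-day enrollment. There is no bias if draws stay in the shared target window, and a downward one if only Standard of Care runs late.

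These sizes rest on assumed late shares, even spread within windows, constant incidence and scheduled draws only. Appendices E and F also call for a blood sample after a positive test. Seroconversions found at that draw would not depend on the Month 4 window, and they are not modelled here.

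The primary PCR endpoint is not affected, since daily swabs run through D113 in both arms.

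**What to change.** If VE against seroconversion is estimated, state one of these in the SAP:

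1. Preferred: a proportional hazards model for interval-censored data, with the event between the last negative and first positive draw. It uses every draw.
2. If Cox regression is kept: nominal visit (Month 2, Month 4) as a discrete time scale, counting a Month 4 draw in either arm only if taken by D141. Participants first drawn later for Month 4 are censored at their last negative qualifying draw.

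Report the Month 4 draw-day distribution by arm in either case, and apply the same rule to the serology component of Secondary Objective 8.

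The cost is analysis wording, with no new data. Option 2 discards Immediate draws after D141. Both options assume that the timing of a draw is unrelated to infection status.

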6.4.3.1 Primary VE Analysis

For the primary analysis, Cox proportional hazards regression will be used to estimate vaccine efficacy against SARS-CoV-2 infection among baseline SARS-CoV-2 seronegative participants, as measured by one minus the hazard ratio (HR) in the Immediate Vaccination vs. Standard of Care arms. This analysis that restricts attention to randomized participants will be supported by a co-primary analysis that combines data from the Standard of Care arm with data from the Vaccine Declined Group. An additional supportive analysis will restrict to the D29- set, counting only infection events diagnosed post-Day 29. These analyses supporting the primary objectives of the study will be detailed in the SAP. To improve precision when comparing randomized groups, and to avoid bias when including non-randomized participants, primary analyses will adjust for an SAP-specified set of “risk” variables, or a composite risk score based on them, that are potentially associated with SARS-CoV-2 exposure including demographics and behaviors captured using the risk assessment tool. Inference will be based on a 2-sided score-based CI and 2-sided score-test for $H_0: VE = 0\%$ with a type 1 error rate of 0.05, although primary interest is in estimation as opposed to hypothesis testing and the study is designed to ensure that the lower limit for the CI will lie above 30% with high probability under $VE > 60\%$. The baseline hazard function in the Cox model will be stratified by study site and randomization stratum, which improves precision of the VE estimate and accounts for the fact that SARS-CoV-2 infection incidence may vary widely across study sites. Description of the risk variables under consideration and of the derivation of a risk score based on them will be described in the study SAP.

The potential impacts of the open-label and observational aspects of the study design will be factored into the choice of efficacy analysis. If there is evidence of differential retention of study participants across groups, or differential adherence to study procedures affecting ascertainment of endpoints such as collection of daily swabs, the analyses will adjust for the differential censoring distribution across groups- as well as potentially informative censoring- as described in the study SAP. At a minimum, these analyses will be performed as sensitivity analyses, complementing the primary analyses described above.

Variables captured using the risk assessment tool and potentially associated with exposure will be compared across groups over study follow-up. If there is evidence that their distributions differ between groups over time, sensitivity analysis will additionally adjust for time-dependent exposure-related variables.

The proportional hazards assumption will be evaluated using methods of Grambsch and Therneau (51).

6.4.3.2 Secondary VE Analyses

The primary analysis of VE against SARS-CoV-2 infection will be repeated in the FAS and D29- sets but including baseline seropositive participants [Secondary Objective 5]; and in the PP set [Secondary Objective 9]. The same methods also apply to evaluating VE against seroconversion [Secondary Objective 2] and VE against COVID-19 disease [Secondary Objective 3]. Additional secondary VE analyses will be conducted where the time of SARS-CoV-2 infection diagnosis is defined as the earliest of the first positive SARS-CoV-2 test result based on either PCR testing of nasal swabs or external SARS-CoV-2 testing.

While the primary analysis of VE against SARS-CoV-2 infection will censor the follow-up time of participants who receive outside COVID-19 vaccination at the time of first outside vaccination, a secondary analysis will be performed that includes infection events and person-time that accrue following outside vaccination with the Moderna COVID-19 Vaccine. Participants receiving outside vaccination other than Moderna COVID-19 Vaccine will continue to be censored at the time of outside vaccination. A time-varying Cox model will be used for inference, per methods in the study SAP.

The asymptomatic SARS-CoV-2 infection endpoint [Secondary Endpoint 8] is defined by the PCR tests of daily swabs and serologic diagnostic testing schedule at month 0, 2, and 4. The occurrence of a COVID-19 disease event is a competing risk because the occurrence of COVID-19 disease precludes the possibility of occurrence of a subsequent asymptomatic SARS-CoV-2 infection event. Therefore, VE against asymptomatic SARS-CoV-2 infection will be assessed using methods accounting for COVID-19 disease as a competing risk. The SAP will provide details.

Vaccine efficacy against the infection and disease endpoints as measured by the reduction in the cumulative incidence of the endpoint by Month 4, will also be evaluated using the Nelson-Aalen estimator of cumulative incidence. This analysis does not rely on the proportional hazards assumption and has a simple interpretation that lends itself to understanding of population effects.

6.4.4 VL analyses

Primary analyses of the vaccine effect on VL will focus on the primary VL endpoint, peak log10 viral load, and will condition on SARS-CoV-2 infection status. Peak log10 viral load will be estimated by the observed maximum log10 viral load measure; secondary VL analyses will employ parametric models to estimate VL at peak. The mean observed log10 viral load will be compared between the Immediate Vaccination and Standard of Care arms. This analysis that restricts attention to randomized participants will be supported by a co-primary

analysis that combines data from the Standard of Care arm with data from the Vaccine Declined Group. Both analyses will use methods that adjust for baseline covariates and covariates at the time of SARS-CoV-2 infection diagnosis, per the study SAP. The covariate adjustment is used to control for potential post-randomization selection bias and lack of comparability between randomized participants and those in the observed cohort, whereby SARS-CoV-2 infected participants in the vaccinated and unvaccinated groups are not comparable in ways that are associated with the VL endpoint. Importantly, this bias occurs when there are factors that modify VE against SARS-CoV-2 infection *and* that are associated with the VL endpoint. An additional supportive analysis will restrict to SARS-CoV-2 infections in the D29- set. Full details around the analysis plan will be specified in the study SAP.

Secondary analyses of vaccine effects on VL will consider a set of other summary measures of the VL curve, each of which have merits for further characterizing the vaccine effect. These include a model-based estimate of peak log₁₀ viral load, duration of detection of virus [estimated empirically or alternatively based on a model fit to the viral load curve], area under the log viral load curve [AUC] calculated using the trapezoidal rule, and area under the portion of the log viral load curve over 10⁵ viral copies/mL. Some mathematical modeling studies provide evidence of transmission potential for VL above this threshold (21), but there is considerable uncertainty and therefore other thresholds will be considered. Analysis methods will be the same as for the primary VL endpoint above.

In addition, the above VL endpoints will be evaluated using unconditional analyses, ie, not conditioning on SARS-CoV-2 infection status, among all enrolled main study participants. Participants not diagnosed with SARS-CoV-2 infection will have an endpoint value defined for analysis, typically a value of zero. The ‘transmission potential’ endpoint [Secondary endpoint 4] is one such endpoint that is defined unconditionally. The merit of unconditional analyses is that they are not subject to potential post-randomization selection bias. A disadvantage of the unconditional analyses is that they may have lower statistical power.

An additional VL endpoint that will be studied is a censored event-time variable, time to VL above 10⁵ copies/mL. This endpoint is defined for all enrolled main study participants and will be analyzed using the same methods used to evaluate VE against SARS-CoV-2 infection, but only counting infections once VL is above 10⁵ copies/mL. Additional methods of analysis that allow for the uncertainty in the level of virus that is associated with transmission will be considered.

Sensitivity analyses for VL will include data from all SARS-CoV-2 infected participants diagnosed based on PCR testing of study swabs or based on outside testing.

The study SAP will detail the secondary analysis approaches for the VL endpoints.

